4. SELECTION AND ENROLLMENT OF PARTICIPANTS

We will accomplish the aims by recruiting 240 Jewish and Arab Women (>18 years) who have been diagnosed with breast cancer and have completed chemotherapy and are still undergoing some form of treatment, to include adjuvant treatment or within 5 years of completing chemotherapy, surgery and/ or radiation therapy. There is evidence that elevated depression, anxiety, fatigue and pain continue over 5 years of survivorship. We plan to recruit 50% Jewish women and 50% Arab women (30% more than represented both in general society and in the cancer population), for comparison. We plan to identify and approach women as they come in for their simulation visit to Radiation Oncology as this usually occurs about a week before radiation therapy starts and will be a good time to obtain baseline measures, however each site nurse will have the freedom to recruit patients who fit the enrollment criteria at other stages of treatment, after chemotherapy. The site nurse will be in charge of identifying and recruiting appropriate candidates for the trial and will use a screening log in order to document reasons for ineligibility or non-participation for eligible candidates.

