4.1 Inclusion Criteria

1) adult (>18) females with initial or recurrent BC; 2) study entry within one year of diagnosis and 3 months after adjuvant cancer care (chemotherapy and radiotherapy (RT)) or reconstructive surgery; any additional or replacement standard medical treatment for cancer is allowed (i.e., surgery, chemotherapy, radiotherapy, neo-adjuvant chemotherapy, endocrine therapy); 4) additional medication is allowed, excluding what is described in exclusion criteria, and will be assessed for potential inclusion as a covariate; 5) can complete assessments in Arabic or Hebrew; 6) provides informed consent.

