5.3 Concomitant Interventions

5.3.1 Allowed Interventions

Any standard medical treatment for cancer is allowed (i.e., surgery, chemotherapy, radiotherapy,

neo-adjuvant chemotherapy, endocrine therapy). However, participants should not be on chemotherapeutic agents during the study period.

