6. STUDY PROCEDURES

6.1 Schedule of Evaluations

Assessment	Screening Visit-1 (Day-14 to Day-1)	Baseline Visit 1 (Day 0)	Tx Visit 2 (W1)	Tx Visit 3 (W2)	Tx Visit 4 (W3)	Tx Visit 5 (W4)	Tx Visit 6 (W5)	Tx Visit 7 (W6)	Tx Visit 8 (W7)	Tx Visit 9 (W8)	Tx Visit 10 (W9)	Follow-up Final Visit (W16)
Verbal consent	X											
Informed Consent Form		X										
Demographics	X											X
Medical Chart Review	X											
Current Medications	X	X										
Inclusion/Exclusion Criteria	X											
Enrollment/ Randomization		X										
Adverse Events		X	X	X	X	X	X	X	X	X	X	
Questionnaires		X								X	X	
Heart measurement rate		X								X	X	
Blood draw		X								X		

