Specifically, models will be tested where condition (AT versus Mandala) predicts the change in emotion processing or physiological correlates (path a) and the change in emotion processing or physiological correlates predicts the change in symptoms (path b). Mediation will be tested by calculating the indirect effect as the product of coefficients (path a x path b) and utilizing bootstrapping to calculate 95% confidence intervals and statistical significance¹³⁰.

Hypothesis 2: changes in emotion processing and cholinergic anti-inflammatory processes will be correlated and have unique effects will be tested by expanding the path analyses from Hypothesis 1 to simultaneously include all proposed mediators on each symptom outcome. Indirect effects with bootstrapped confidence intervals will be calculated as before. The change in mediators will be allowed to freely correlate to examine their relations.

[figure not shown]

Figure 3: Model hypotheses 1 & 2

The Exploratory Hypothesis posits a sequential mediation model from treatment (AT versus Mandala) to emotion processing (path a) to cholinergic anti-inflammatory processes (path b) and finally to symptoms (path c). To establish temporal precedence, change in emotion processing from baseline to intervention midpoint and change in cholinergic anti-inflammatory processes from intervention midpoint to completion, and change in symptoms from baseline to intervention completion will be used. Indirect effects will be calculated as the product of three coefficients (path a x path b x path c) capturing the hypothesized sequentially mediated effect. Bootstrapped confidence intervals and significance tests will be calculated. To test the reverse ordering, the same process will be used exchanging the time points and order of emotion processing and cholinergic anti-inflammatory processes.

[figure not shown]

Figure 4: Model Hypothesis 3

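### Radiotherapy may fall between baseline and T2 for some women and not others, and the SAP text for the mechanism-to-symptom path has no term for it, so a shared radiotherapy effect on the physiological mediators and on fatigue or pain could be read as mediation

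*SAP*

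**What the plan says.** **Mediation test.** In SAP C.5.2, second part of Hypothesis 1, condition predicts change in the mechanism (path a), and "the change in emotion processing or physiological correlates predicts the change in symptoms (path b"). The product a × b is tested with a bootstrap 95% interval. Hypothesis 2 puts all mediators into the same model. The text names no covariate for these models. The diagram (SAP Figure 3) is missing from the text available for this review. The only covariate the SAP names is traditional values, in the Hypothesis 3 mixed model.

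**Recruitment.** Protocol section 4 plans to approach women at the radiotherapy simulation visit because "this usually occurs about a week before radiation therapy starts and will be a good time to obtain baseline measures". It adds that "each site nurse will have the freedom to recruit patients who fit the enrollment criteria at other stages of treatment, after chemotherapy".

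**Eligibility and allowed treatment.** Section 4.1 asks for "study entry within one year of diagnosis and 3 months after adjuvant cancer care (chemotherapy and radiotherapy (RT)) or reconstructive surgery", and in the same item lists radiotherapy among the additional treatments allowed. Section 5.3.1 says: "Any standard medical treatment for cancer is allowed (i.e., surgery, chemotherapy, radiotherapy".

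**Timing.** Section 6.2.2 puts randomisation straight after baseline and one week before an 8-week intervention.

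**Data capture.** In section 6.1, "Medical Chart Review" is marked at screening only, and current medications at screening and baseline only. Sections 4.1 and 4.2 foresee accounting for medication and for recent infection or dental work. Neither names radiotherapy as something to adjust for.

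**The concern.** Randomisation protects path a. It does not protect path b, which is an observational association between two changes measured in the same women. Any event between baseline and T2 that moves both changes, and that some women have and others do not, creates such an association.

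Radiotherapy is a candidate that the protocol itself places next to baseline. It could plausibly move cytokines or HRV and also fatigue or pain. If art therapy does change the mediator, an association produced only by radiotherapy makes a × b differ from zero, and the trial reports a mechanism that is not there. Mediation is the stated purpose of the study. If radiotherapy raised a pro-inflammatory marker and symptoms together while art therapy lowered the marker, the error would point in the direction of the hypothesis.

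The protocol already treats infection and dental work as outside influences on these measures. Radiotherapy is not on that list, and the schedule has no item that would capture it after baseline.

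**Working it through.** **1. The plan's own figure.** SAP C.5.1 and protocol 8.2 state more than 90% power with 240 women (120 per arm). Recomputed at two-sided 5%:
- path a, d = 0.50: 97.2%
- path b, r = 0.30 (Fisher z): 99.7%
- indirect effect, both paths significant: 0.972 × 0.997 = 97.0%; 96% by bootstrap simulation.

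With 15% attrition (240 × 0.85 = 204) these are 94.6%, 99.2% and 93.9%. The stated power reproduces and is not in question.

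**2. Inputs for the bias.** From the documents: N = 240, 1:1, and path a d = 0.50. Assumed, because the documents are silent: a share p of women has radiotherapy in the change interval; it shifts mediator change and symptom change by the same g (in residual SD); the mediator has no true effect on symptoms (b = 0). The SAP does not define the change interval for Hypotheses 1 and 2; baseline to T2 is assumed.

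**3. Induced correlation.** With v = p(1 − p)g², the correlation given condition is r = v/(1 + v). For p = 0.5:
- g = 0.3: 0.0225/1.0225 = 0.022
- g = 0.5: 0.0625/1.0625 = 0.059
- g = 0.8: 0.16/1.16 = 0.138

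**4. From correlation to false mediation.** For p = 0.5, g = 0.8:
- Path b: z = atanh(0.138) × √237 = 2.14, so it is significant with probability about Φ(2.14 − 1.96) = 0.57.
- Path a: radiotherapy adds variance to the mediator, so z = 0.50/√1.16 × √60 = 3.60, giving Φ(3.60 − 1.96) = 0.95.
- Both: 0.57 × 0.95 = 0.54.

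The same formulas (both tails kept) for other shares; p and 1 − p give the same value:

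| Radiotherapy share | g = 0.3 | g = 0.5 | g = 0.8 |
|---|---|---|---|
| 10% or 90% | 5% | 6% | 13% |
| 25% or 75% | 6% | 10% | 36% |
| 50% | 6% | 14% | 54% |

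**5. Simulation.** With 4,000 runs per case, requiring both paths significant and path b adjusted for condition, the rates at p = 0.5 were 6.0%, 13.8% and 53.7%. With a radiotherapy indicator in both equations they were 4.8%, 5.2% and 4.8%. At 10% or 90% they were 4–5%, 6% and 12–14%.

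A smaller simulation with the SAP's bootstrap of a × b (300 trials, Monte Carlo error about 1 to 3 points) gave, at p = 0.5, 5.0%, 11.3% and 58.7% unadjusted and 4.0%, 3.7% and 4.3% adjusted. At p = 0.25 it gave 11.7% (0.5 SD) and 38.0% (0.8 SD), falling to 5.0% and 7.7%.

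**6. Boundary cases.**
- All women have identical radiotherapy: 5.7% with or without the term, so no bias.
- Art therapy does not change the mediator (a = 0), g = 0.8: 3.0%, so no inflation.
- a = 0.2 and p = 0.5: 5% at 0.5 SD and 18% at 0.8 SD.

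**The case against.** The strongest objection is that the eligibility criterion may remove the problem. If section 4.1 means at least three months after radiotherapy, planned adjuvant radiotherapy is over before baseline. That reading is open, but the same item lists radiotherapy as allowed additional treatment, 5.3.1 allows it during the study, and section 4 plans recruitment just before it starts. The documents do not settle which applies. A reader might infer that all women are enrolled a week before radiotherapy. The text does not support that either: it is a plan with freedom to recruit at other stages.

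Even for women met at simulation, radiotherapy inside the interval is inferred. Section 3 expects each cohort to take about a month to a month and a half to collect, so a woman approached early could be well into radiotherapy by baseline, unless the 14-day limit from screening to baseline holds. This stands as uncertainty about the share.

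Four further limits also stand:
- Figure 3 might show covariates. Only the SAP text can be said to name none.
- A 50% share maximises p(1 − p), and the 54% also needs 0.8 SD shifts on both changes and d = 0.50 on the mediator. A reader might take 54% as the expected error rate; nothing in the documents supports that.
- The absence of a scheduled chart review does not mean that radiotherapy dates are lost. Hospital charts may still hold them.
- Surgery and endocrine therapy are allowed too, so radiotherapy is one of several possible confounders. The return to about 5% occurs because the simulation has a single, perfectly measured confounder.

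None of this gives path b a term for treatment received between baseline and T2.

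**Conclusion.** The point holds in a limited form. On the text as it stands, radiotherapy may fall in the change interval for some women and not others, path b is unadjusted, and no scheduled item records the exposure. False mediation then ranges from about nominal (5–6% at 0.3 SD shared shifts, whatever the share) through 6–14% at 0.5 SD to 12–54% at 0.8 SD. The lower ends belong to shares of 10% or 90% and the upper ends to 50%. Share and shifts are assumptions; the true size cannot be known from the documents.

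The result rests on three conditions: radiotherapy differs between women, it moves both mediator and symptom, and art therapy truly changes the mediator. If any one fails, this inflation disappears.

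A reader might extend the point to the primary Time × Condition comparisons or to path a. Both are protected by randomisation. A reader might also extend it to emotion processing or depression, but a plausible radiotherapy route is argued here only for cytokines and HRV with fatigue and pain. The change is worth making because it is cheap and bears on the trial's central question.

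**What to change.** 1. Reconcile protocol sections 4, 4.1 and 5.3.1 on when women may enter relative to radiotherapy and whether it may occur on study, and state the change interval for the Hypothesis 1 and 2 path models.
2. Record radiotherapy start and end dates from the chart at T2 and T3.
3. Add radiotherapy within the change interval as a covariate in both the mediator and the symptom equations of those models, above all for the physiological mediators. Report the unadjusted model alongside.
4. Add a sensitivity analysis for remaining unmeasured mediator–outcome confounding, since one indicator does not remove all of it.

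Cost: one chart field at two visits, one degree of freedom per equation, and a small amount of extra data entry and analysis. The dates are best collected as the trial runs, because the present schedule would leave them to be retrieved afterwards.

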3. STUDY DESIGN

We will accomplish the aims by a randomized controlled trial of 240 Jewish and Arab women (>18 years) who have been diagnosed with BC and have completed chemotherapy, recruited in Israel and randomized to undergo an 8-week (1.5 hours per week) program of group Art Therapy compared to women who will be designated to an 8-week sham Art Therapy group. We chose this design to be able to isolate and examine emotional processing and the effect of enhancing emotional processing on HRV and inflammatory cytokines and examine how these may mediate the effect of art therapy on depressive symptoms, pain and fatigue.

The primary outcomes are emotion processing, comprised of emotion awareness, expression and acceptance and the cholinergic anti-inflammatory pathway, comprised of resting HRV and inflammatory (pro and regulatory) cytokines. The secondary outcome measures are depression, pain and fatigue.

The study will take place at the cancer centers of 3 study sites: Rabin Medical Center, Rambam Medical Center and Ziv Medical Center, the enrollment period will vary until each cohort is collected and is expected to be approximately a month or a month and a half.

The interventions will be administered by an experienced Art Therapist who will be trained in this specific protocol by the PI [name] who is an Art Therapy [name] intervention is designed to follow the Bodymind model of AT⁶². Each session will start with a ten-minute rapport building and touching base and continue with 50 minutes of art making in a calm and supportive environment. Art materials are on the table and after the art therapist provides a brief explanation of the use of the materials; participants are encouraged to explore and experience as they wish. The art therapist is present to guide and assist. Participants are encouraged to minimize conversation; instrumental music is played to encourage introspective experiences. The session ends with 30 minutes of processing and discussion in which each participant shares and briefly presents their work and group participants can respond and or provide support.

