**NCT03377816: The Role of Emotional Processing in Improving the Quality of Life of
Breast Cancer Patients (REPAT)**

Statistical Analysis Plan- September 14th, 2017

The following statistical analysis plan was written in September of 2017 as part of the grant proposal for the REPAT study and was incorporated into the study protocol and guided the design of the actual study.

C.5 Statistical Methods:

C.5.1 Sample Size: A power analysis was conducted via Monte Carlo simulation in Mplus showed that a sample size of 240 (120 per condition), provides: (1) >90% power to detect a moderate effect size (Cohen's $d = 0.50$) of treatment on mechanisms, (2) >90% power to detect a moderate association ($r = 0.30$) between mechanisms and symptoms, and (3) >90% power to detect an indirect effect from treatment to symptoms via mechanisms. The sample size will also provide >80% power to detect a moderate effect size for the Condition by Ethno-Cultural group interaction.

C.5.2 Data Analysis: Prior to testing hypotheses, we will produce a thorough descriptive profile of the sample and examine the distributions of key variables involved in the hypotheses. We will also examine levels of nonresponse and **missing data**. Prior experience indicates attrition will be low; although, some missing data are expected due to missed assessments and dropout. Data will be analyzed using full information maximum likelihood to address missing data, supplemented with pattern-mixture modeling for non-random missingness. The first part of Hypothesis 1: women in the AT group experience greater increases in emotion processing, HRV, and regulatory cytokine levels and greater decreases in pro-inflammatory cytokines than women randomized to the Mandala condition will be tested using linear mixed models¹²⁹. Models will include a Time x Condition interaction to test whether the change over time in emotion processing and cholinergic anti-inflammatory processes is significantly different between treatment groups.

A significant interaction will be followed up by simple slope tests to characterize the degree of change separately in the AT and Mandala conditions.

The second part of Hypothesis 1: emotion processing and cholinergic anti-inflammatory processes mediate the effects of AT on symptoms (depression, pain, fatigue) will be tested using path analysis.

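### Mediation is tested through 6 to 33 or more indirect effects, each at its own 95% interval, with no primary effect, order or adjustment

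*SAP*

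**What the plan says.** The second part of Hypothesis 1 in SAP C.5.2 states that "emotion processing and cholinergic anti-inflammatory processes mediate the effects of AT on symptoms (depression, pain, fatigue) will be tested using path analysis". Condition predicts change in the mediator (path a), change in the mediator predicts change in the symptom (path b), and the product is judged by "utilizing bootstrapping to calculate 95% confidence intervals and statistical significance". Hypothesis 2 extends these models to "simultaneously include all proposed mediators on each symptom outcome", again with bootstrapped intervals for the indirect effects. Of the mediation models, only the sequential one is labelled exploratory.

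Protocol section 1 makes both mechanisms the object of the study. Section 3 lists them as primary outcomes: emotion processing (awareness, expression, acceptance), and the cholinergic pathway (resting HRV and cytokines). It then adds: "The secondary outcome measures are depression, pain and fatigue". Section 6.2.2 lists seven cytokines and two pain instruments (BCPT and PROMIS). Section 6.2.4 repeats the assessments after the intervention and again eight weeks later.

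SAP C.5.1 says that "a sample size of 240 (120 per condition), provides" three things relevant here: ">90% power to detect a moderate effect size (Cohen's $d = 0.50$) of treatment on mechanisms", ">90% power to detect a moderate association ($r = 0.30$) between mechanisms and symptoms" and ">90% power to detect an indirect effect from treatment to symptoms via mechanisms".

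Neither document states an overall alpha, a primary indirect effect, a testing order or a multiplicity adjustment. The text of the path models names mediators only at construct level and does not say whether components enter singly or as composites.

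**The concern.** Mediation is the question that the trial was designed and partly sized to answer. If each mediator–symptom pair is judged alone, any one significant pair could be reported as the way art therapy works. Pairs could also disagree, with no rule for which one decides.

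Controlling the Time x Condition tests would not solve this. That control guards only against a null path a. Once art therapy really moves a mediator, the test of the product becomes roughly a 5% test of path b, repeated for every pair.

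**Working it through.** **Inputs.** N = 240, 120 per arm, d = 0.50 and r = 0.30 (SAP C.5.1); 15% attrition (Protocol, Sample Size and Population); two-sided 0.05 per effect, implied by the 95% interval. The documents give no correlations among mediators or among symptoms, so these are assumed and varied from 0 to 0.7. The type of bootstrap is also unstated; percentile is assumed.

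**Step 1. Reproduce the stated power** (normal approximation).
- Path a: 0.50 × √(120/2) = 3.873; Φ(3.873 − 1.960) = 97.2%.
- Path b: atanh(0.30) × √237 = 4.765; Φ(4.765 − 1.960) = 99.7%.
- Indirect effect, both paths significant: 0.972 × 0.997 = 97.0%.
- After 15% loss, 240 × 0.85 = 204: 94.6% × 99.2% = 93.9%.

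All agree with the plan's >90% for a single indirect effect.

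**Step 2. Count the effects.**
- Two constructs × 3 symptoms = 6.
- One emotion score, HRV, regulatory cytokines and pro-inflammatory cytokines: 4 × 3 = 12.
- Three emotion domains + HRV + 7 cytokines = 11; 11 × 3 = 33.
- Five emotion scores (awareness, two emotional-approach subscales, avoidance, acceptance) + HRV + 7 cytokines = 13; with both pain scales, 13 × 4 = 52.

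**Step 3. Error per pair.** With d = 0.50 on path a and path b = 0, the expected rate is 0.05 × 0.972 = 4.9%. Simulation gives 4.7–5.1% with the joint-significance test (path b adjusted for condition) and 5.3% with a percentile bootstrap.

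**Step 4. Chance of at least one false indirect effect, all mediators moved by d = 0.50, path b = 0 everywhere.** The independence bound is 1 − 0.95^k. The simulated column assumes correlation 0.3 among mediators and 0.5 among symptoms.

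| Tests (k) | Independence bound | Simulated |
|---|---|---|
| 6 | 26% | 22% |
| 12 | 46% | 38% |
| 33 | 82% | 68% |
| 52 | 93% | 83% |

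For 33 tests at other correlations (mediators/symptoms), simulation gives 80% at 0/0, 60% at 0.5/0.5 and 42% at 0.7/0.7. The bootstrap check gives 84% at 0/0, 72% at 0.3/0.5 and 64% at 0.5/0.5. Adding the Hypothesis 2 models to the 33 gives 76–88% over the same grid.

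**Step 5. Weaker response, 33 tests.**
- Only three of eleven mediators move by d = 0.50: 28–36%.
- All move by d = 0.2: 28% at correlations 0.5/0.5, 34% at 0.3/0.5.
- Both paths null everywhere: 4–7%.

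**Step 6. Hypothesised direction only.** With 33 tests, all mediators at d = 0.50 and symptom correlation 0.5, the chance is 49%, 39%, 32% and 25% at mediator correlations 0, 0.3, 0.5 and 0.7. It is 11% for 6 tests, and 15% for 33 tests if three mediators move. The halving weakens only near full independence: 1 − (1 − 0.025 × 0.972)^33 = 56%, against 81% two-sided.

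**Step 7. Power under the remedy.** Holm over six starts at 0.05/6 = 0.0083. With the noncentral t for path a, slightly more conservative than Step 1, power is 88.6% × 98.3% = 87% at N = 240 and 81.6% × 96.0% = 78% at n = 204. The first test in a fixed order keeps the Step 1 values of 97% and 94%.

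**The case against.** The strongest reply concerns the count. The SAP never says that components are tested one at a time. Its Figure 3, the diagram of the Hypothesis 1 and 2 models, was missing from the text copy available here, and it may show two constructs only. A reader might infer that the plan commits to 33 tests. The documents do not support that: 33 follows from the named components, but 6 is also a possible reading.

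A reader might also infer that a false mechanism claim is about 60% likely, or more likely than not, in the setting the trial expects. That does not follow. The 60% needs all eleven mediators, each cytokine included, to move by d = 0.50, path b to be zero for every pair, and correlations of 0.5. The plan itself assumes r = 0.30 between mechanisms and symptoms, so it does not expect path b to be zero. The hypotheses are also directional, and about half of the false pairs would point the wrong way; at those correlations the directional figure is 32%.

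Finally, symptoms are secondary outcomes in a study described as mechanistic, so how strictly to control error over their mediation is partly a matter of judgement.

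These points limit the size of the problem but do not remove it. Even 6 tests give about 22% two-sided. Reaching 6 requires composites that the SAP text does not define, and a single physiological score must reconcile cytokines predicted to move in opposite directions. Mediation is in the stated objectives and the power statement, and Hypotheses 1 and 2 carry no exploratory label.

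**Conclusion.** The point holds in this form: the family of indirect effects is undefined, each member is judged at its own 95% interval, and nothing says which result decides. If all mediators respond at d = 0.50 and none drives symptoms, the two-sided chance of at least one false indirect effect is about 22% for 6 tests and about 40–80% for 33, and about half that in the hypothesised direction in most settings. It falls to about 30% for 33 tests when few mediators respond or all respond weakly, and to 4–7% when both paths are null. Hypothesis 2 adds to the first two figures.

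These sizes rest on assumed correlations, an assumed bootstrap type and a count that the SAP leaves open. The missing decision rule depends on none of them. The analysis remains usable, and the plan should be amended.

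**What to change.** In SAP C.5.2, name a short confirmatory set that keeps both mechanisms of Protocol sections 1 and 3. One example is one emotion-processing score and one pre-defined physiological mediator, each against depression, pain and fatigue: 2 x 3 = 6 effects. The physiological mediator could be resting HRV, or a cytokine score with components signed in their hypothesised directions. State how each score is built.

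Fix one pain scale and one time point; otherwise selection remains inside each test. Apply Holm across the six effects, or state a fixed order that stops at the first non-significant result. Label all other pairs and the Hypothesis 2 unique effects exploratory.

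This changes wording only; it needs no new data or patients. Individual cytokine and subscale pairs could still be reported, but not as confirmatory. Under Holm over six, the >90% indirect-effect power must be restated: about 87% at the strictest step with N = 240, and about 78% at n = 204 after 15% loss. A fixed order keeps about 97% (94% at n = 204) for the first test, but later effects can be claimed only if every earlier one succeeds.
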